2.2.1.3. Clinical Development of Entinostat

Potential Drug Interactions: Metabolism: Data from *in vitro* metabolism experiments in human tissues demonstrated that entinostat is not metabolized by CYP enzymes⁴⁷, but UGT 1A4 did metabolize entinostat to its M2 glucuronide metabolite. No metabolites could be detected after incubation of entinostat in human liver microsomes⁴⁷. While inhibition of CYP enzymes 2B6 and 3A4 was seen, the data show that the degree of the inhibition makes it unlikely that any *in vivo* systemic interactions would occur. Intestinal CYP 3A4 may be inhibited by entinostat. However, entinostat did not inhibit any UGT enzymes tested. Entinostat was found to induce CYP 1A2, CYP 2C6, and CYP 2B8 as well as UGT 1A4. Finally, entinostat was found to be a substrate for P-gp and BCRP transporters, but did not inhibit either of these transport proteins.

Patient Care Implications:

Entinostat may cause fatigue or malaise; advise patient to exercise caution while driving a vehicle or operating machinery.

Administration of entinostat is contraindicated in patients with a history of allergy to entinostat or other medications that have a benzamide structure (eg, tiapride, remoxipride, clebropride).

Careful monitoring of patients for signs of infection or reactivation of past infections is recommended, as reactivation of infection has been reported in patients treated with entinostat, in some cases without evidence of neutropenia. The clinical significance of this finding and the potential association with entinostat is unknown.

Entinostat must not be used during pregnancy or while breast-feeding. Women and men participating in entinostat clinical studies must agree to use acceptable contraceptive methods, as indicated in the clinical study protocol, during treatment and for 4 months thereafter.

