3.1.2 Age ≥ 18 years

Because no dosing or adverse event data are currently available on the use of entinostat in combination with pembrolizumab (MK-3475) in patients <18 years of age, children are excluded from this study, but will be eligible for future pediatric trials.

3.1.3 ECOG performance status ≤ 2 ([Appendix C](#)).

3.1.4 Patients must have laboratory test results within these ranges:

- Calculated creatinine clearance by MDRD (CrCl) $= >60$ ml/min/1.73 squared meter
- Total bilirubin ≤ 2.0 mg/dL unless due to Gilbert's syndrome, hemolysis, or ineffective hematopoiesis and AST (SGOT) and ALT (SGPT) $\leq 3 \times$ ULN

3.1.5 Females of childbearing potential must have a negative serum or urine pregnancy test within 72 hours prior to start of first cycle of therapy.

- Patients must have no clinical evidence of CNS or pulmonary leukostasis, disseminated intravascular coagulation, or CNS leukemia.
- Patients must have no serious or uncontrolled medical conditions

3.1.6 The effects of entinostat and pembrolizumab (MK-3475) on the developing human fetus are unknown. For this reason, women of child-bearing potential and men who are sexually active with women of childbearing potential must agree to use adequate contraception (hormonal or barrier method of birth control; abstinence) prior to study entry and for the duration of study participation. Should a woman become pregnant or suspect she is pregnant while she or her partner is participating in this study, she should inform her treating physician immediately. Men who are sexually active with women of childbearing potential, treated or enrolled on this protocol must also agree to use adequate contraception prior to the study, for the duration of study participation, and 4 months after completion of entinostat and MK3475 (pembrolizumab) administration.

3.1.7 Ability to understand and the willingness to sign a written informed consent document.

3.1.8 Patients, who relapsed 6 months after bone marrow transplant and have no evidence of active graft versus host disease and are off systemic immunosuppressant medications for at least 2 months and have received HMA therapy before or after transplant and meet other eligibility criteria of progression after at least 4 months of DNMTi therapy, are eligible to be enrolled in this clinical trial.

3.1.9 Patients who are Human Immunodeficiency Virus (HIV) positive may participate IF they meet the following eligibility requirements:

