4.3.2 OPEN/IWRS User Requirements

OPEN/IWRS users must meet the following requirements:

- Have a valid CTEP-IAM account (*i.e.*, CTEP username and password).
- To enroll patients or request slot reservations: Be on an ETCTN Corresponding or Participating Organization roster with the role of Registrar. Registrars must hold a minimum of an AP registration type.
- To approve slot reservations or access cohort management: Be identified to Theradex as the “Client Admin” for the study.
- Have regulatory approval for the conduct of the study at their site.

Prior to accessing OPEN/IWRS, site staff should verify the following:

- All eligibility criteria have been met within the protocol stated timeframes.
- If applicable, all patients have signed an appropriate consent form and HIPAA authorization form.

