
An additional dose level (DL -1) in which day 8 of ENT will be omitted (i.e. ENT at 8mg on D1, and pembrolizumab (MK-3475) at 200mg IV on D1 of 21-day cycles) will be used if 2 or more patients develop DLT during the first 2 cycles of combined therapy at DL1. If 0 or 1 patients of the 6 patients treated with combined therapy at DL-1 develop DLT then DL-1 will be used in the second part of the study. If 2 or more 6 patients enrolled in DL -1 develop

DLT, then the study will be terminated.

Toxicities will be tabulated and graded according to the Common Terminology Criteria for Adverse Events Version 5 (CTCAE-5). DLT will be assessed after the first 2 cycles of combined therapy. Responses will be as defined by IWG-2006 criteria (CR, PR, or HI) and assessed at the end of the combined first 2 cycles, and every 2 cycles afterwards. Patients who achieve an objective response or maintain a stable disease (SD) status after the first 4 combination cycles will continue receiving both drugs at the same schedule till progression up to 1 year of combined therapy.

PART 2: After the safe dose of the combination is established, 15 patients will be treated with ENT+ pembrolizumab (MK-3475) combination at that same dose and schedule. Assessment of response will occur after 4 combination cycles and similar to part 1, those who achieve an objective response or SD will continue to receive the therapy till progression. Patients who progress or respond and subsequently lose response will be withdrawn from study. BM biopsy/aspirate and PB samples will be done at baseline, after first cycle of ENT monotherapy, every 2 cycles of combined therapy, and at time of progression or study discontinuation. Formal safety assessment will be performed after the first 6 patients are enrolled and each have received at least 5 cycles (i.e. 1 ENT monotherapy cycle and 4 cycles of combined therapy (DL1, DL2) for each patient) to assess for any unexpected autoimmune or other toxicity. In all the phases of the study, entinostat will be administered in clinic within 2 hours before administration of pembrolizumab (MK-3475). Entinostat will be stored at the pharmacy and it will not be given for the patient to take home.

Dose Escalation Schedule		
Dose Level	Dose*	
	Entinostat	MK-3475 - Pembrolizumab
Level -1(Backup dose level)	8mg po D1	200mg
Level 1 (starting dose level)	8mg po D1,8	200mg
Level 2	8mg po D1,8,15	200mg

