5.5 Duration of Therapy

In the absence of treatment delays due to adverse event(s), treatment may continue for one year (maximum 18 cycles or entinostat and maximum 17 cycles of pembrolizumab (MK-3475)) or until one of the following criteria applies:

- Disease progression as defined in modified IWG-2006 ([Appendix A1](#), [Appendix A2](#)) for MDS
- If disease has shown evidence of progression based on an increase in the blast counts according to the modified IWG-2006, but the patient is otherwise clinically stable and his transfusion requirement have not changed, the investigator can give two additional cycles of combined treatment and bone marrow biopsy will be repeated after that cycle. If repeat bone marrow biopsy confirms disease progression, the patient will be taken off the trial.
- Intercurrent illness that prevents further administration of treatment
- Patient decides to withdraw from the study
- General or specific changes in the patient's condition render the patient unacceptable for further treatment in the judgment of the investigator

- Clinical progression
- Patient non-compliance
- Pregnancy
 - All women of child bearing potential should be instructed to contact the investigator immediately if they suspect they might be pregnant (e.g., missed or late menstrual period) at any time during study participation.
 - The investigator must immediately notify CTEP in the event of a confirmed pregnancy in a patient participating in the study.
- Termination of the study by sponsor
- The drug manufacturer can no longer provide the study agent
- Unacceptable adverse event(s), including:
 - Any Grade 2 drug-related uveitis or eye pain or blurred vision that does not respond to topical therapy and does not improve to Grade 1 severity within the re-treatment period OR requires systemic treatment.
 - Grade 3 drug-related autoimmune or inflammatory event including uveitis, pneumonitis, diarrhea, colitis, neurologic adverse events, hypersensitivity reaction, or infusion reaction of any duration requires discontinuation.
 - Any Grade 3 or 4 drug-related laboratory imbalance or electrolyte abnormality, not associated with underlying organ pathology and that do not require treatment except for electrolyte replacements, do not require treatment discontinuation, with the following exceptions with approval of the Principal Investigator:

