7.7 Reporting of Pregnancy and Lactation to the Sponsor

Although pregnancy and lactation are not considered adverse events, it is the responsibility of investigators or their designees to report any pregnancy or lactation in a subject (spontaneously reported to them) that occurs during the trial or within 120 days of completing the trial, or 30 days following cessation of treatment if the subject initiates new anticancer therapy, whichever is earlier. All subjects who become pregnant must be followed to the completion/termination of the pregnancy. Pregnancy outcomes of spontaneous abortion, missed abortion, benign hydatidiform mole, blighted ovum, pregnancy loss, intrauterine death, miscarriage and stillbirth must be reported as serious events (Important Medical Events). If the pregnancy continues to term, the outcome (health of infant) must also be reported.

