- An unscheduled visit can occur at any time during the study. Source must be maintained for these unscheduled visits. The date for the visit and any data generated must be recorded on the appropriate CRF. Source documents for these unscheduled visits must also be maintained. In cases of aplasia, CBCs will be performed weekly and Bone marrow aspirates and biopsies will be performed every 3 months until recovery.

1: Hematology assessment includes complete blood count and differential blood count.

2: Chemistry assessment includes serum sodium, potassium, chloride, carbon dioxide, serum urea nitrogen, creatinine, calcium, glucose, alkaline phosphatase, AST, ALT, total bilirubin, total protein, albumin. Blood samples for LFTs must be collected and analyzed at local or central labs within 3 days prior to dosing. LFT results must be reviewed by the principal investigator (or designee) to meet dosing criteria specifications: $\leq 3 \times$ ULN for AST, ALT and $\leq 2 \times$ ULN for Total bilirubin unless liver metastases are present in which case LFT $\leq 5 \times$ ULN for AST, ALT and Total bilirubin $\leq 3.0 \times$ ULN) prior to dosing. If, during the course of treatment abnormal LFT values are detected, entinostat and Pembrolizumab (MK-3475) will not be administered. The subject should be evaluated and managed referring to the protocol, as clinically appropriate.

In addition, evaluation for pituitary function must be made prior to each infusion either by clinical history, TSH or both.

3: Pregnancy tests for females of childbearing potential. A female of childbearing potential is a sexually mature female who: 1) has not undergone a hysterectomy or bilateral oophorectomy; or 2) has not been naturally postmenopausal for at least 24 consecutive months (i.e., has had menses at any time in the preceding 24 consecutive months).

4: An additional safety assessment will be done before each maintenance dose.

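### Section 3.1.6 gives women of childbearing potential no contraception period after treatment, although it gives men 4 months and the entinostat sections require 4 months for both sexes

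*Combined protocol and SAP*

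**What the plan says.** Section 3.1.6 has two contraception sentences. The first covers women of childbearing potential and men who are sexually active with such women. It requires contraception "prior to study entry and for the duration of study participation". The second covers men only and requires it "for the duration of study participation, and 4 months after completion of entinostat and MK3475 (pembrolizumab) administration".

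Sections 2.2.1.3 and 8.1.1, both about entinostat, say that women and men in entinostat studies "must agree to use acceptable contraceptive methods, as indicated in the clinical study protocol, during treatment and for 4 months thereafter".

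Section 4.3.2 has site staff confirm before enrolment that "All eligibility criteria have been met within the protocol stated timeframes". Section 5.5 tells women of childbearing potential to contact the investigator if they suspect pregnancy ("e.g., missed or late menstrual period) at any time during study participation"). Section 7.7 requires reporting of pregnancies that patients mention while they are on trial and for a limited time afterwards, which it sets as follows: "within 120 days of completing the trial, or 30 days following cessation of treatment if the subject initiates new anticancer therapy, whichever is earlier".

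**The concern.** Section 3.1.6 is the only eligibility criterion in the available text that sets a contraception duty. The synopsis criteria and the exclusions in 3.2 set none. A site that screens and counsels from it would find a period after treatment for men and none for women.

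The stake is fetal exposure. Section 3.1.6 calls the fetal effects of both drugs unknown, and 2.2.1.3 and 8.1.1 bar entinostat in pregnancy. The Section 10 calendar schedules pregnancy testing at screening only, so no planned test would detect a pregnancy after treatment. Nothing in the design, endpoints or analysis depends on this.

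**Working it through.** The plan gives no figure to reproduce. The check is a comparison of texts, followed by simple arithmetic on durations.

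**1. Stated period after treatment**

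| Section | Women | Men |
|---|---|---|
| 3.1.6 (eligibility) | none stated | 4 months after both drugs |
| 2.2.1.3 (entinostat background) | 4 months | 4 months |
| 8.1.1 (entinostat pharmaceutical information) | 4 months | 4 months |

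**2. Does study participation already cover the 4 months?** The term is not defined.

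- For a broad meaning: 5.6 follows patients for 6 months after the last dose and speaks of follow-up as a phase of the study. Section 14.1.3 describes patients who remain enrolled only for follow-up.
- For a narrow meaning: the men's sentence lists the 4 months in addition to participation, which would be redundant if participation ran 6 months past the last dose. Section 5.6 and the Section 10 calendar both place monthly follow-up after removal from study. Section 5.1, Part 2, says "Patients who progress or respond and subsequently lose response will be withdrawn from study".

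The text leans towards the narrow meaning but does not settle it.

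**3. Size of the shortfall per woman**

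- 4 months = 4 × 365.25/12 = 121.75, about 122 days.
- Broad meaning: 6 months of follow-up exceeds 4 months, so the shortfall is 0.
- Narrow meaning, with the site also applying 8.1.1 from the end of all treatment: 0.
- Narrow meaning, with 3.1.6 used alone and removal on the day of the last dose: about 122 days. If removal comes *t* days after the last dose, the shortfall is 122 − *t*.

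**4. Does 8.1.1 fully close the gap?** It is an entinostat section, and the pembrolizumab sections (2.2.1 and 8.1.2) contain no contraception instruction. The synopsis allows a patient who stops one drug for a clearly attributed event to stay on the other. Suppose a site counts the 4 months from the last entinostat dose, and the last pembrolizumab dose comes *k* 21-day cycles later. The cover left after pembrolizumab is then 121.75 − 21*k* days. It reaches zero at *k* = 121.75/21 = 5.8, so six such cycles use it up.

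**5. Is exposure after the last dose plausible?** The pharmacokinetics text (Section 2.1.2.1) gives a pembrolizumab half-life of about 4 weeks. Assuming simple exponential decline, the fraction remaining is 0.5 after 28 days and 0.5^(122/28) = 0.5^4.36 ≈ 0.05 at 122 days. Most of the decline therefore falls within the period on which 3.1.6 is silent for women.

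**6. Is the reporting rule in 7.7 a substitute?** It covers reporting, not prevention. If new anticancer therapy starts, it can end 30 days after treatment stops, which leaves 121.75 − 30 = 91.75, about 92 of the 122 days, with no reporting duty.

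**The case against.** The strongest reply is that the protocol already contains the requirement. Sections 2.2.1.3 and 8.1.1 are mandatory, name women, and state 4 months. Their reference to the study protocol is most naturally read as attaching to the contraceptive methods, so the period stands by itself. A site that applies 8.1.1 leaves little or no gap. This stands, and it is why the point is an omission and not a contradiction. It does not remove the problem, because the verified criterion remains shorter for women and 8.1.1 concerns entinostat only.

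Second, participation may include follow-up, which would give women about 6 months. That reading is open. Being withdrawn or removed from study does not by itself show where participation ends, and the men's sentence may simply be a redundant addition. What remains is an undefined term carrying a fetal-safety duty.

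Third, the worst case needs several conditions together: a woman of childbearing potential, a site relying on 3.1.6 alone, the narrow meaning, and a consent form that does not fill the gap. The consent form and patient handout were not available for review, so what women are actually told cannot be judged. Section 5.6 also provides at least monthly contact for 6 months, a further partial safeguard. These points limit the likely harm. They do not explain why the criterion should differ between the sexes.

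**Conclusion.** The concern holds. Section 3.1.6 states no period after treatment for women, and its wording falls short of the protocol's own 4-month requirement. The shortfall is 0 to about 122 days per woman, depending on how a site reads participation and whether it also applies 8.1.1. The upper end assumes that 3.1.6 is used alone and that participation ends at removal on the day of the last dose.

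The number of women of childbearing potential is not given. It is probably small: Section 2.1 describes typically advanced age, and footnote 3 of the Section 10 calendar counts a woman with a uterus and ovaries as of childbearing potential only if she "has not been naturally postmenopausal for at least 24 consecutive months". The difference in wording is certain; actual early release of a woman is possible but not shown. This should be corrected for participant safety. It has no bearing on the trial's statistical conclusions.

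**What to change.** In 3.1.6, extend the men's requirement to women of childbearing potential: contraception before entry, throughout the study, and for at least 4 months after the last dose of entinostat or pembrolizumab, whichever is later, regardless of withdrawal or removal from study. Tying the period to the later drug also covers a woman who continues on pembrolizumab alone.

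Check that the consent form and the patient handout in Appendix E say the same. The cost is one sentence and that check, with no change to design, sample size or analysis.

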3.2 Exclusion Criteria

3.2.1. Any patients eligible for allo-SCT and willing to undergo allo-SCT as determined at time of screening for trial. Patients who are ineligible or not interested in undergoing allo-SCT will be eligible for the trial.

3.2.2. Any serious medical condition, uncontrolled intercurrent illness (e.g., active infection, symptomatic CHF, unstable angina, cardiac arrhythmias, laboratory abnormalities, or psychiatric illness and/or biopsychosocial conditions that may limit compliance

3.2.3. Patients with known active cancers who are on therapy for those cancers at time of screening.

3.2.4. Patients with a known positive test for hepatitis B virus surface antigen (HBV sAg) or hepatitis C virus ribonucleic acid (HCV antibody) indicating acute or chronic infection might be enrolled if the viral load by PCR is undetectable with/without active treatment.

3.2.5. Pregnant or breast feeding females (lactating females must agree not to breast feed while taking the study drugs)

- 3.2.6. Use of any other experimental drug or therapy within 21 days of baseline - patients who have had chemotherapy or radiotherapy within 4 weeks of entering the study or those who have not recovered from adverse events due to agents administered more than 4 weeks earlier
- 3.2.7. Known hypersensitivity to pembrolizumab (MK-3475) or history of allergic reactions to compounds of similar chemical or biologic composition to anti-PD1 or PD-L1 antibodies or entinostat.
- 3.2.8. Prior treatment with any anti-PD-1 blocking therapies or HDACi, or anti-CTLA-4 antibody, CD137 agonist or other immune activating therapy such as anti-CD 40 antibody within the last 3 months of enrollment in the study.
- 3.2.9. Any history of active or severe autoimmune disease: Inflammatory bowel disease, including ulcerative colitis and Crohn's Disease, rheumatoid arthritis, systemic progressive scleroderma, systemic lupus erythematosus, autoimmune vasculitis (e.g., Wegener's Granulomatosis), CNS or motor neuropathy considered of autoimmune origin (e.g. Guillain-Barre Syndrome, myasthenia gravis, multiple sclerosis). Patients with hypothyroidism with stable hormone replacement therapy dosing are allowed on study.
- 3.2.10. Has a history of (non-infectious) pneumonitis that required steroids or has current pneumonitis

3.3 Inclusion of Women and Minorities

NIH policy requires that women and members of minority groups and their subpopulations be included in all NIH-supported biomedical and behavioral research projects involving NIH-defined clinical research unless a clear and compelling rationale and justification establishes to the satisfaction of the funding Institute & Center (IC) Director that inclusion is inappropriate with respect to the health of the subjects or the purpose of the research. Exclusion under other circumstances must be designated by the Director, NIH, upon the recommendation of an IC Director based on a compelling rationale and justification. Cost is not an acceptable reason for exclusion except when the study would duplicate data from other sources. Women of childbearing potential should not be routinely excluded from participation in clinical research. Please see <http://grants.nih.gov/grants/funding/phs398/phs398.pdf>.

